#### 7.2.2 Exclusion criteria

Patients fulfilling any of the following criteria are not eligible for this study:

- 1. Patient having other eye diseases that could compromise the VA.
- 2. Patient with existing or suspected ocular or periocular infection in the study eye.
- 3. Patient with an existing intraocular inflammation (IOI).
- 4. Patient with uncontrolled glaucoma defined as intraocular pressure > 25 mmHg despite treatment with anti-glaucoma medication, or according to Investigator's judgment.
- 5. Patient who has undergone intraocular surgery within 3 months prior to enrollment in this study.
- 6. Patient having scar, fibrosis and atrophy involving the center of the fovea in the study eye.

#### 7.3 Variables

#### 7.3.1 Demography and Baseline characteristics

Patient demographics, medical history will be done at the first visit at the time of screening (

Table 7-1). Patient demographic and baseline characteristic data taken at study entry will include: date of birth, gender, race, ethnicity, weight and height, smoking history, history of ocular disease (diagnosis of nAMD and any other ocular conditions), other relevant medical histories (significant medical conditions and surgical events), treatment for nAMD received in the 12 months prior to study entry.

Concomitant medications will be summarized by Anatomical Therapeutic Chemical (ATC) class and preferred term according to the WHO-DRL dictionary.

#### 7.3.2 Physical examination

The physical exam will consist of a routine evaluation of organ systems e.g., ears, eyes, nose, throat, neck, lymph nodes, lungs, heart, abdomen, skin/extremities, neurological, and musculoskeletal systems.

Information for all physical examinations will be included in the source documentation at the study site. Clinically relevant findings that are present prior to initiating treatment with brolucizumab 6 mg injection must be included in the appropriate section of the CRF.

#### 7.3.3 Vital signs

Vital signs including blood pressure (BP), heart rate, systolic (SBP) and diastolic blood pressure (DBP) will be measured when the patient has been sitting for approximately five minutes. If an automated blood pressure device is used, it should be calibrated according to the manufacturer's guidelines.

#### 7.3.4 Effectiveness variables

- 1. Visual acuity (VA) in ETDRS letter
- 2. Number of brolucizumab injections for treatment during study duration
- 3. q8w and q12w injection interval
- 4. Intra-retinal fluid (IRF) and Sub-retinal fluid (SRF)
- 5. Central subfield thickness (CST)

#### 7.3.5 Safety variables

#### Adverse events (AEs) and serious adverse events (SAEs) reporting

Treatment-emergent changes in any of the ocular parameters, which meet the definition of an Adverse Event (serious and non-serious), will be recorded in the appropriate section of the CRF.

Any significant changes in the vital signs and/or physical examination parameters observed after first administration of brolucizumab which meet the definition of an Adverse Event will be recorded in the appropriate section of the CRF.

#### Exposure of interest

Exposure to study medication from start to end of treatment within this interventional study. The number (%) of patients who discontinue prematurely prior to 56 weeks with including the

reasons for discontinuation. Furthermore, the number of injections will be presented for the total study period.

#### 7.3.6 Data sources

Information on brolucizumab administration since treatment start will be recorded in the Case Report/Case Record Form (CRF). All concomitant medications including the reason for prescribing the medication and the start and end dates will be recorded on the concomitant medications/significant non-drug therapies CRF.

Initiation of the participating sites will be performed by Novartis and/or a designated Contract Research Organization (CRO).

Sites enrolling subjects in this study will record data on eCRFs provided by Novartis. A designated CRO will capture, check, store and analyze the data.

Concomitant or prior medications entered into the database will be coded using the World Health Organization (WHO) Drug Reference List. Medical history/current medical conditions and adverse events will be coded using the MedDRA terminology.

#### 7.3.7 Data collection schedule

Data originating from routine patient visits and assessments at study time points (Baseline, i.e. start of brolucizumab treatment, and approximately week 4, week 8, week 16, week 20, week 24, week 32, week 40, week 44, week 48 and at week 56 post-initiation of treatment/or discontinuation of treatment) and safety data (AEs and SAEs, see Section 8) from any time point during the duration of the study will be recorded for the purpose of this study. Data will be collected only on the eye treated with brolucizumab and if both eyes are treated with brolucizumab, the data from one eye (study eye) will be recorded. The selection of eye (study eye) will be as per discretion of the Investigator at the time of enrolment in this study.

Participation in this prospective interventional study and confirmation of patient consent to collect and use patient data will be documented using an informed consent form by the site staff on or before the baseline visit. A copy of this signed document will be given to the patient and the original will remain in the patient's records.

Each patient is uniquely identified in the study by a combination of the Investigator's center number and a patient number. The center number is assigned by Novartis (or designee), the patient number is assigned by the Investigator. At each site, the first patient is assigned patient number 1, and subsequent patients are assigned consecutive numbers (e.g., the second patient is assigned patient number 2; the third patient is assigned patient number 3, and so forth). Once assigned to a patient, the patient number will not be reused.

Visit number	1	2	3	4	5	6	7	8	9	10	11
Time of visit [Week (Wk)]	Wk 0	Wk 4±1	Wk 8±1	Wk 16±1	Wk 20±1	Wk 24±1	Wk 32±1	Wk 40±1	Wk 44±1	Wk 48±1	Wk 56 (Follow-up) EOS
Inclusion/ Exclusion Criteria	Х										
Informed consent	Х										
Demographics and Baseline Characteristics	X										
Physical Examination	Х										
Vital Signs	Х										
Brolucizumab	Х	Х	X	X*	X #	X*	X*#	X*	X#	X*	
BCVA	Х	Х	Х	X*#	X #	X*	X*#	X*	X #	X*	X
ІОР	Х	Х	Х	X*#	X #	X*	X*#	X*	X #	X*	Х
Fundus photography	Х			X*#			X*#				Х
ОСТ	Х	Х	Х	X*#	X #	X*	X*#	X*	X #	X*	X
Fluorescein Angiography (FA)	X										Х
Adverse Events	Х	Х	X	X*#	X #	X*	X*#	X*	X #	X*	X

Table 7-1	Data collection	
-----------	-----------------	--

\* - q8w dosing

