#### 7.2.1 Inclusion criteria

- 1. Female or male, treatment naïve patient with ≥50 years of age, with neovascular agerelated macular degeneration (nAMD).
- 2. Patient or legally acceptable representative (LAR) willing to voluntarily provide signed informed consent for participation in the study.

Note: In case where both eyes are affected, data of only one eye ['study eye'] will be recorded. Selection of the eye to be considered for the purpose of the study [referred to as 'study eye'] will be as per the Investigator's discretion.

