#### 9.1 Adverse events (AE)

Information about all AEs, whether volunteered by the patient, discovered by Investigator questioning, or detected through physical examination, laboratory test or other means, will be collected and recorded on an Adverse Event Case Report Form and will be followed up as appropriate.

An AE is any undesirable sign, symptom or medical condition occurring after starting study treatment, even if the event is not considered to be treatment-related. Study treatment includes the study medication under evaluation, and any reference or placebo drug (or therapy) given during any phase of the trial.

Confidential

Medical conditions/diseases present before starting study treatment will only be considered adverse events if they worsen after starting study treatment (any procedures specified in the protocol). Adverse events (but not serious adverse events) occurring before starting study treatment but after signing the informed consent form will be recorded on the Medical History/Current Medical Conditions Case.

For surveillance/monitoring of signs and symptoms related to Intra-ocular inflammation following initial injections of brolucizumab, the recommendations as mentioned below need to be followed by the study Investigator:

- After Injecting brolucizumab, inform the patient about the symptoms of intra-ocular inflammation [eye pain, eye redness, blurred/decreased vision, dark, floating spots in the vision (floaters), light sensitivity, flashes, scotoma (blind spot in vision)].
- And inform the patient to report immediately if he/she sees/experiences any of the signs/symptoms as mentioned above.
- When IOI, retinal vasculitis, and/or RAO is present or suspected during a visit, investigators must perform thorough ophthalmic examination, and will conduct OCT, fluorescein angiography and color fundus photography (preferably wide-field or with peripheral sweeps).
- These additional assessments will be documented in the source and appropriate eCRF pages as applicable.
- Follow-up the patient in the first week after injection to look for/assess symptoms (Phone call/Visit).
- An adverse event management protocol/mitigation plan would be provided to all the investigators to manage an event of intra-ocular inflammation.

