#### 9.2 Serious Adverse Events (SAEs)

Information about all serious adverse events will be collected and recorded on the Serious Adverse Event Report Form. To ensure patient safety each serious adverse event will also be reported to Novartis Patient Safety within 24 hours of the Investigator learning of its occurrence.

An SAE is defined as an event which:

- Is fatal or life-threatening
- Results in persistent or significant disability/incapacity
- Constitutes a congenital anomaly/birth defect
- Requires inpatient hospitalization or prolongation of existing hospitalization, unless hospitalization is for:
  - routine treatment or monitoring of the studied indication, not associated with any deterioration in condition (specify what this includes);
  - Elective or pre-planned treatment for a pre-existing condition that is unrelated to the indication under study and has not worsened since the start of the drug of interest; or
  - social reasons and respite care in the absence of any deterioration in the patient's general condition.
- Is medically significant, i.e., defined as an event that jeopardizes the patient or may require medical or surgical intervention to prevent one of the outcomes listed above e.g. may require treatment on an emergency outpatient basis for an event not fulfilling any of the definitions of a SAE given above and not resulting in hospital admission
- Transmission of an infectious agent via medicinal product

Any SAEs exempt from this reporting process must be clearly identified in the study protocol with a scientific/medical justification e.g. SAEs due to disease progression, SAEs due to a planned surgical procedure, etc. Any SAE study protocol exemptions MUST be agreed with the respective country health authority as part of the protocol approval process. This confirmation by the HA must be recorded and kept on file for the study concerned.

Any SAE occurring after the patient has provided informed consent and until 4 weeks after the patient has stopped study participation will be reported. Serious adverse events occurring more than 4 weeks after study discontinuation will be reported to Novartis Patient Safety only if a relationship with the study therapy is suspected by the Investigator.

As far as possible, each SAE will also be described by (but not limited to):

- its duration (onset date = date of 1st signs or symptoms, and end dates);
- the seriousness criteria and severity if applicable (mild, moderate, severe);

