#### Derivation:

- Timeframe: The first brolucizumab administration date to Visit 11 (week 56)
- If the question from eCRF, "Treatment Emergent AE" = "Yes", then corresponding events will be considered as TEAEs.
- Ocular and systemic AEs.
- If the question from eCRF, "Relationship with study drug" = "Yes", then corresponding events will be considered as suspected AEs related to the study medication.
- If the question from eCRF, "Was the adverse event serious" = "Yes", then corresponding events will be considered as serious AEs.
- If the question from eCRF, "What is the outcome of this adverse event" = "Fatal", then corresponding events will be considered as AEs leading to death.
- If the question, "Primary Reasons for Discontinuation" = "Adverse event", then corresponding events will be considered as AEs leading to discontinuation from the study.

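### Protocol 7.3.7 and 7.2.1 conflict with 9.1 and 9.2 on whether non-serious ocular adverse events in a brolucizumab-treated fellow eye are recorded, and SAP 19.1.1 does not say how ocular events are identified or attributed by eye

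*Protocol*

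**What the plan says.** Two passages limit recording to one eye:

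- Protocol 7.3.7 (Data collection schedule): "if both eyes are treated with brolucizumab, the data from one eye (study eye) will be recorded".
- Protocol 7.2.1 (note under the inclusion criteria): "In case where both eyes are affected, data of only one eye ['study eye'] will be recorded".

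Three passages ask for safety data with no restriction by eye:

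- Protocol 7.3.7, in the sentence just before the one-eye rule: "safety data (AEs and SAEs, see Section 8) from any time point during the duration of the study will be recorded".
- Protocol 9.1: "Information about all AEs, whether volunteered by the patient, discovered by Investigator questioning, or detected through physical examination".
- Protocol 9.2: "Information about all serious adverse events will be collected and recorded on the Serious Adverse Event Report Form".

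On analysis, the primary objective (Protocol 6.1) is ocular and non-ocular safety. Protocol 7.6.5 plans AE incidence by MedDRA class and term, plus rates per treatment year. In SAP 19.1.1 the derivation for this component is one bare line, "Ocular and systemic AEs". By contrast, the BCVA derivations in SAP 20.1 to 20.3 name the study eye.

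**The concern.** The one-eye rule follows directly after a sentence that covers both visit data and safety data, and it makes no exception for AEs. Table 7-1, in the same section, has an Adverse Events row. A site could therefore reasonably keep ocular AEs to the study eye, while another site working from Section 9 would record them for both eyes. The cross-reference that might settle the matter sends the reader to Section 8, which is protection of human subjects; safety monitoring is Section 9.

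An ocular event in a fellow eye treated with brolucizumab is an event on study drug, in a study whose primary endpoint is safety. The protocol plans 10 centres. If they read the rule differently, the ocular count becomes a mixture of two definitions, and nothing in the SAP would separate them.

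**Working it through.** **Step 1: the recording rules side by side.**

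- Systemic AEs: 9.1 requires them. No sensible reading of the one-eye rule removes them.
- Study-eye ocular AEs: recorded under every passage.
- Serious fellow-eye ocular events: 9.2 and 9.2.1 require all SAEs, to be reported within 24 hours, with no eye limit. The route is explicit.
- Non-serious fellow-eye ocular AEs: 9.1 says record; 7.3.7 and 7.2.1, taken literally, say do not. This is where the conflict bites.

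**Step 2: the analysis rules.** SAP 19.1.1 gives an eCRF question for TEAEs and for related, serious, fatal and discontinuation events, but none for ocular events. Neither SAP 15 nor SAP 19 has a rule for study eye against fellow eye. SAP 20.4 counts one injection per treatment visit without naming the eye, so injections into both eyes on one day would count once. Protocol 7.6.4 measures exposure as days from start to end of treatment, again without naming an eye.

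**Step 3: size if the one-eye rule is applied to AEs.** The plan gives no figure for this, and no share of patients treated in both eyes. Assumptions:

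- n patients, each with one study eye
- a share b of patients whose fellow eye is also treated
- the same event rate p in every treated eye
- every site uses the AE-excluding reading

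Expected events in treated eyes = n·p·(1 + b). Recorded events = n·p. Share missed = b/(1 + b); n and p cancel.

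- b = 0: 0%
- b = 5%: 0.05/1.05 = 4.8%
- b = 10%: 0.10/1.10 = 9.1% (with 105 patients, 10.5 of 115.5 treated eyes)
- b = 20%: 0.20/1.20 = 16.7% (21 of 126 treated eyes)
- b = 30%: 0.30/1.30 = 23.1%

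These are shares of events. For the number of patients with an ocular event, the share missed lies between zero (the two eyes always have events together) and the same b/(1 + b) (they never do). Serious events that arrive through 9.2 reduce it further.

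**Step 4: size if sites record both eyes.** If events from both eyes are divided by one eye's time, and the eyes have equal follow-up, the result is (1 + b) times the rate per eye-year: 1.10 times at b = 10% and 1.20 times at b = 20%. This concerns only the per-treatment-year rates of Protocol 7.6.5.

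**The case against.** The best defence is that the one-eye rule was never meant for AEs. Its opening words confine data collection to the treated eye. Applied literally to safety data, they would bar all systemic AEs and contradict the primary objective. The rule reads more naturally as governing eye assessments: BCVA, IOP, OCT, fundus photography and angiography. Protocol 7.3.5 speaks of changes in any ocular parameter without naming an eye, and the surveillance for intra-ocular inflammation in 9.1 is not limited to the study eye. Protocol 7.3.6 records brolucizumab administration and all concomitant medication, also without an eye limit. SAP 20.9 shows that right or left eye is held for at least some assessments. The eCRF is not among the documents and some SAP pages were not available, so the AE form may already carry laterality.

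Most of this stands, and it shows that exclusion is not the most natural reading. It does not show that the text says so. The rule has no stated scope, the cross-reference goes to the wrong section, and a site could confine ocular AEs to the study eye while still recording systemic ones. A laterality field would reduce the data work but would not supply the missing SAP rule.

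It is also fair to say that the SAP's main statistic does not need an eye denominator. SAP 19.1.2 reports patients, percentages and events in the FAS, and a patient with an event in either eye is properly counted over patients.

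**Conclusion.** The point stands as a conflict between passages together with a missing analysis rule. Protocol 7.3.7 and 7.2.1 do not agree with 9.1 and 9.2 about non-serious ocular AEs in a treated fellow eye, and SAP 19.1.1 leaves ocular AEs without a means of identification or attribution. Because one of the conflicting passages is a stated recording rule, a site that follows it can produce a wrong count. This is more than absent detail.

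The size depends on a bilateral-treatment share that the documents do not give. The 9% to 17% range is an illustration for a share of 10% to 20%, and it is the most that could be missed at those shares under equal per-eye rates, since it supposes that every site excludes fellow-eye AEs.

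Three stronger conclusions might be inferred, and the documents do not support them:

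- That the plan excludes fellow-eye AEs. Sections 9.1 and 9.2 give them an unrestricted route.
- That fellow-eye injections go unrecorded. Section 7.3.6 has no eye limit.
- That the primary incidence lacks a valid denominator. The patient-level percentage is coherent; the denominator problem is confined to the rates per treatment year.

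**What to change.** - **Protocol 7.2.1 and 7.3.7:** state that the one-eye rule covers effectiveness and eye-assessment data only, and that AEs and SAEs in either eye are recorded under 9.1 and 9.2. Correct the cross-reference from Section 8 to Section 9.
- **Data:** capture or query AE laterality and the dates of any fellow-eye brolucizumab injections, where the eCRF does not already hold them.
- **SAP 19.1:** identify ocular AEs by MedDRA term. Identifying them by whether laterality was entered would lose events where that field is blank. Keep patient-level incidence as primary. Add a display of ocular AEs by study eye and fellow eye (treated or untreated), with unknown laterality as its own category. State the eye basis of any rate per treatment year.

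The cost is moderate. SAP 8.1 says that all 105 patients were already enrolled, so some queries would be retrospective, although Protocol 7.7.2 requires source documents to be kept. If the clarification is handled as a protocol amendment, Protocol 8 requires sponsor agreement and ethics approval. The analysis itself needs one extra table split.

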# - q12w dosing

*Note:* If the patient comes up at an unscheduled visit or more frequently, his/her BCVA should be measured as for the other visits.

#### 7.4 Study size

The sample size of this interventional study is based on statistical consideration. The current study proposes to recruit 105 patients.

For calculating sample size, safety results of the Phase 3 studies (Dugel 2020) were used. From these studies, the adverse event rate for relevant adverse events is assumed to be approximately 1/100.

The sample size was estimated empirically using 1000 replicates for each sample size between 10 and 250 participants. The number of patients was selected to ensure at least a 90% probability that at least one of these rare adverse events will be observed in the study, which will allow the development of a comprehensive safety profile within the Indian population specifically.

Estimated sample size: N = 95

Additional 10% sample required for patient attrition over 56 weeks (dropouts/lost to follow-up).

Total sample size required: N = 105

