#### Study size

The sample size of this interventional study will be 105 considering 10% dropouts/lost to follow-up. The actual estimated sample size is 95.

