#### 8. Statistical considerations

#### 8.1 Multicentre studies

The study plans to enrol a total of 105 patients in 11 centres. 105 patients have been enrolled from 10 initiated sites.

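### With 95 patients, the chance of seeing at least one adverse event of rate 1/100 is about 62%, not the stated 90% or more, and this is the trial's only sample-size justification

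*Protocol*

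**What the plan says.** Protocol section 7.4 takes its planning rate from the Phase 3 studies: "the adverse event rate for relevant adverse events is assumed to be approximately 1/100". It describes the method as a simulation: "The sample size was estimated empirically using 1000 replicates for each sample size between 10 and 250 participants". The criterion was "at least a 90% probability that at least one of these rare adverse events will be observed in the study", and the protocol adds that this will support a full safety profile in Indian patients. The result is "Estimated sample size: N = 95". A further 10% for attrition over 56 weeks leads to "Total sample size required: N = 105".

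The abstract, under Study size, repeats the figure: "The actual estimated sample size is 95". SAP section 8.1 gives the target of 105 and states that "105 patients have been enrolled from 10 initiated sites"; it offers no other reasoning for the size. Neither document has a power or precision statement for any endpoint.

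**The concern.** The probability of seeing at least one event is fixed once the rate and the number of patients are known. A 1% rate and 95 patients imply fewer than one expected event (0.95), which cannot give a 90% chance of seeing one.

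This matters because safety is the primary objective, treatment-emergent adverse events are the primary endpoint, and the study answers a post-marketing commitment to the Indian health authority. A reader told 90% would take the absence of a given rare event as fairly strong evidence that its rate is below 1%. If the real figure is nearer 60%, that inference is not available. The planned analysis would not correct the impression: SAP section 19.1.2 reports patients, percentages and event counts, and specifies no confidence interval.

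**Working it through.** **Inputs** (Protocol 7.4): rate p = 0.01; target probability 0.90; evaluable n = 95; enrolled n = 105; simulation with 1000 replicates at each n from 10 to 250.

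**Step from 95 to 105.** 95 × 1.10 = 104.5, rounded up to 105. Dividing instead gives 95/0.90 = 105.6, or 106. The attrition step is sound within rounding, so the problem lies in the 95.

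**Probability of at least one event**, P = 1 − (1 − p)^n:
- n = 95: 1 − 0.99^95 = 61.5%, so the chance of seeing none is 38.5%.
- n = 105: 1 − 0.99^105 = 65.2%, so the chance of seeing none is 34.8%.

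**Sample size needed for 90%.** n = ln(0.10)/ln(0.99) = 229.1, so 230 (229 gives 89.99%, 230 gives 90.09%). This lies inside the protocol's own search range.

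**Rate at which the plan's n does give 90%.** p = 1 − 0.10^(1/n): 2.4% for n = 95 and 2.2% for n = 105.

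**Could another reading rescue the figure?**
- *Simulation error.* At n = 95 the standard error of a 1000-replicate estimate is √(0.615 × 0.385/1000) = 1.5 points. The shortfall is 90 − 61.5 = 28.5 points, over 18 standard errors. In 20,000 simulated estimates at n = 95, the range was 55.7% to 68.4%.
- *The search as described.* In 500 repeats of the search from 10 to 250, the first n to reach 90% had a median of 219 and ranged from 198 to 233.
- *A looser 1/100.* At n = 95, a rate of 1.5% gives 76.2% and 2.0% gives 85.3%.
- *A yearly rate over 56 weeks.* 1 − exp(−95 × 0.01 × 56/52) = 64.1%; with 105 patients, 67.7%.
- *Several independent event types at 1% each, any one counting.* Two types: 1 − 0.99^190 = 85.2% at n = 95, with 115 patients needed. Three types: 1 − 0.99^285 = 94.3%, with 77 needed. No whole number of types gives 95.

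**What zero events would show.** The two-sided 95% Clopper-Pearson upper limit is 1 − 0.025^(1/n): 3.8% for 0/95 and 3.5% for 0/105.

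**The case against.** The best defence is that section 7.4 speaks of events in the plural and calls the rate approximate. Suppose two independent event types were simulated at slightly above 1% each. Under the protocol's search, two types at 1.15% first cross 90% at a median n of 97 (95% range 91 to 101), and two at 1.2% at a median of 93 (87 to 97). So 95 could have come from such a run. This is possible, but it does not rescue the statement. The protocol gives no number of types and no such rate. The exact probability at n = 95 would still be 88.9% or 89.9%, short of the promised minimum. The combined rate would also be 1 − 0.988² = 2.4% in the second case, so the 90% would describe a pooled event more than twice as common as the one stated.

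Three other points carry some weight:
- The full analysis set counts every treated patient, so 65.2% is closer to the actual trial than 61.5%. It is an upper figure, because patients who leave early are followed for less time.
- The primary analysis is descriptive and the 90% enters no test, so no planned result changes.
- The SAP promises 95% intervals for key results (section 7.5) and names Clopper-Pearson (section 7.4). It does not apply either to the adverse event analysis in section 19.

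**Conclusion.** The concern holds. On the protocol's stated rate, 95 patients give a 61.5% chance of observing at least one event and 105 give 65.2%, against a claim of at least 90%. The chance of missing a 1% event entirely is 38.5% or 34.8%, where the plan implies at most 10%. These figures assume one independent chance of the event per patient over the whole study, at 1%. A yearly rate or a moderately higher one does not close the gap. A reading with several event types comes close only with assumptions that the protocol does not state.

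Because this is the sole justification for the size of a trial whose primary purpose is safety, it must be corrected. The size itself need not change.

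**What to change.** 1. Establish and record what was simulated: the rate, the number of event types, and which events count as relevant. If it differed from a single event at 1%, section 7.4 must say so.
2. Unless that record supports something else, restate Protocol 7.4 along these lines: with 95 evaluable patients (105 enrolled), the probability of observing at least one event of true incidence 1% is 61.5% (65.2%); a 90% probability applies to incidences of about 2.4% or more (2.2% for 105). Amend the abstract's Study size paragraph to match, and carry the corrected statement into the study report.
3. Temper the claim about a full safety profile, and state that zero events in 95 patients excludes only rates above 3.8% (3.5% for 105), using the two-sided 95% limit.
4. As a secondary addition, specify in SAP section 19 a two-sided 95% Clopper-Pearson interval for the incidence of the relevant events. This can be programmed only once those events are listed; items 2 and 3 do not depend on it.

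The cost is wording in the protocol, SAP and study report, plus one interval in the tables. No patients or visits are added. The price is a less favourable stated probability.
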